6.6.3. Vital Signs

The measurement taken immediately prior to start of study drug will be used as the baseline for calculating changes in vital signs.

All vital sign data will be descriptively summarized by treatment group within SAS population and reported in accordance with the Pfizer Data Standards for safety reporting.

6.6.4. Electrocardiograms

Central reader will provide the reading of all ECG parameters. Descriptive statistics will be provided for change from baseline to each measurement time for heart rate, PR interval, QRS width, QT interval and QTcF (Fridericia correction) values. Baseline will be defined as the mean of the pre-dose triplicates at the Baseline Visit. Additionally, the incidence of categorical increases in QTc intervals will be provided. Categories for QTcF are \geq 450 msec, \geq 480 msec, and \geq 500 msec. Categories for QTcF as change from baseline are \geq 30 msec increase and \geq 60 msec increase. QTcF is considered the primary QTc value for measurements of change and for clinical decision making as this correction is more accurate with changes in heart rate.

7. INTERIM ANALYSES

7.1. Interim Analyses and Summaries

A planned interim analysis for efficacy and futility with a sample size-re-estimation will be conducted and reviewed by an independent E-DMC after approximately 45% overall participants have completed the Day 28 assessments in the mITT analysis set(ie, 28 days after randomization).

At the time of planning the Phase 2/3 study, there was uncertainty about the rate of COVID-19-related hospitalization or death in the primary analysis population, and about the treatment effect of PF-07321332. Hence, a sample size re-estimation will be conducted during the first interim analysis based on conditional power. The sample size can be adjusted one time and the increase will be capped at 30%. A well-established method described by

PFIZER CONFIDENTIAL
Page 31

Cui, Hung, and Wang (1999)¹ (implemented in EAST 6.5) will be used to control the Type I error probability.²

The nominal significance level for theplanned interim and final proportion of hospitalization/death analyses is determined by means of the Lan-DeMets procedure with an O'Brien-Fleming stopping boundary, with an overall 2-sided type I error rate of 5%.

O'Brien-Fleming approach will be used for decision making, ie, reject H0 with 2-sided p-value ≤ 0.002 , or reject H1 with 2-sided p-value ≥ 0.924 . The final p-value for rejecting H0 will be ≤ 0.049 (2-sided) or reject H1 with 2-sided p-value ≥ 0.049 . The actual stopping boundaries will depend on the exact timing of the interim analysis. If the efficacy boundary is crossed at the interim analysis, a final analysis will be conducted as a supportive analysis.

Before any interim analysis is performed, the details of the objectives, decision criteria, dissemination plan, and method of maintaining the study blind as per Pfizer's SOPs will be documented and approved in the interim analysis SAP.

7.2. Data Monitoring Committee

This study will use a E-DMC. The E-DMC is independent of the study team and includes only external members. The E-DMC charter describes the role of the DMC in more detail.

The E-DMC will be responsible for ongoing monitoring of the efficacy and safety of participants in the study according to the charter. The recommendations made by the E-DMC will be forwarded to the appropriate authorized Pfizer personnel for review and final decision. Pfizer will communicate such decisions, which may include summaries of aggregate analyses of safety data to regulatory authorities, investigators, as appropriate.

7.3. Blinding of the Sponsor

The majority of sponsor staff will be blinded to study intervention allocation. There will be an unblinded team supporting the interactions with, and the analyses for, the E-DMC while the study is ongoing. The team will consist of medical monitor/clinicians, reporting statistician and reporting programmer(s) and will be separate from the direct members of the study team. The reporting team may include designated ad hoc member(s).

After all participants complete the Day 34 visit (or Early Termination (ET) prior to Day 34 visit), the study will be unblinded and analyses through Day 34, including the primary efficacy endpoint analyses, will be conducted. However, a blinded study team will manage the completion of the study until all participants have completed the Week 24 visit (or ET prior to the Week 24 visit). The blinded team will be separate from the unblinded team.

Details of the unblinded sponsor staff supporting the E-DMC and the timing of unblinding will be outlined in the Unblinding Plan.

9. APPENDICES

Appendix 1. Summary of Efficacy Analyses

Endpoint	Analysis Type	Population	Data Inclusion and Rules for Handling Intercurrent Events and Missing Data	Analysis Model
Proportion of participants with COVID-19 related hospitalization or death from any cause through Day 28.	Primary Efficacy analysis	mITT	All data collected will be included regardless of intercurrent events. Kaplan- Meier method to take account of losses to follow-up.	Kaplan-Meier method
Proportion of participants with COVID-19 related hospitalization or death from any cause through Day 28.	Sensitivity analysis for primary endpoint	mITT2	All data collected will be included regardless of intercurrent events. Kaplan-Meier method to take account of losses to follow-up.	Kaplan-Meier
Proportion of participants with COVID-19 related hospitalization or death from any cause through Day 28.	Sensitivity analysis for primary analysis	mITT	Analysis excluding all data from India sites and participants from Site 1470.	Kaplan-Meier method
Proportion of participants with COVID-19 related hospitalization or death from any cause through Day 28.	Sensitivity analysis for primary analysis	mITT	Analysis excluding all participants from Site 1470.	Kaplan-Meier method
Proportion of participants with COVID-19 related hospitalization or death from any cause through Day 28.	Sensitivity analysis for primary analysis	mITT	Analysis excluding participants from the sentinel cohort of the study treated with active treatment (3 doses of 100 mg).	Kaplan-Meier method
Proportion of participants with COVID-19 related hospitalization or death from any cause through Day 28.	Sensitivity analysis for primary analysis	mITT	If the participant's last observed data is prior to Day 21, then impute as an event with event day as day of last observed data +1. If the participant's last observed data is on or after Day 21, do not impute an event and participant remains censored at day of last observed data	Kaplan-Meier method
Proportion of participants with COVID-19 related	Supplemental analysis for primary analysis	mITT	All data collected will be included regardless of intercurrent events.	logistic regression model

Endpoint	Analysis Type	Population	Data Inclusion and Rules for Handling Intercurrent Events and Missing Data	Analysis Model
hospitalization or death from any cause through Day 28.			Use stratification variables as in Section 3.5.	
Proportion of participants with COVID-19 related hospitalization or death from any cause through Day 28.	Supplemental analysis for primary analysis	Completers Analysis	Only data collected are included regardless of intercurrent events. Kaplan- Meier method to take account of losses to follow-up.	Kaplan-Meier method
Proportion of participants with COVID-19 related hospitalization or death from any cause through Day 28.	Supplemental analysis for primary analysis	mITT	In the mITT population, participants that received a therapeutic COVID-19 mAb treatment post-baseline will be considered as an event for the endpoint (in addition to hospitalization and death due to any with mAb treatment date as the time of event). Kaplan- Meier method to take account of losses to follow-up.	Kaplan-Meier method
Proportion of participants with COVID-19 related hospitalization or death from any cause through Day 28.	Primary Efficacy analysis	mITT including only data with first randomization	All data collected will be included regardless of intercurrent events. Kaplan-Meier method to take account of losses to follow-up.	Kaplan-Meier method
Proportion of participants with COVID-19 related hospitalization or death from any cause through Day 28.	Sensitivity analysis for primary endpoint	mITT2 including only data with first randomization	All data collected will be included regardless of intercurrent events. Kaplan-Meier method to take account of losses to follow-up.	Kaplan-Meier
Proportion of participants with COVID-19 related hospitalization or death from any cause through Day 28.	Sensitivity analysis for primary analysis	mITT including only data with first randomization	Analysis excluding all data from India sites and participants from Site 1470.	Kaplan-Meier method
Proportion of participants with COVID-19 related hospitalization or death from any cause through Day 28.	Sensitivity analysis for primary analysis	mITT including only data with first randomization	Analysis excluding all participants from Site 1470.	Kaplan-Meier method

Endpoint	Analysis Type	Population	Data Inclusion and Rules for Handling Intercurrent Events and Missing Data	Analysis Model
Proportion of participants with COVID-19 related hospitalization or death from any cause through Day 28.	Sensitivity analysis for primary analysis	mITT including only data with first randomization	Analysis excluding participants from the sentinel cohort of the study treated with active treatment (3 doses of 100 mg).	Kaplan-Meier method
Proportion of participants with COVID-19 related hospitalization or death from any cause through Day 28.	Sensitivity analysis for primary analysis	mITT including only data with first randomization	If the participant's last observed data is prior to Day 21, then impute as an event with event day as day of last observed data +1. If the participant's last observed data is on or after Day 21, do not impute an event and participant remains censored at day of last observed data.	Kaplan-Meier method
Proportion of participants with COVID-19 related hospitalization or death from any cause through Day 28.	Supplemental analysis for primary analysis	mITT including only data with first randomization	All data collected will be included regardless of intercurrent events. Use stratification variables as in Section 3.5.	logistic regression model
Proportion of participants with COVID-19 related hospitalization or death from any cause through Day 28.	Supplemental analysis for primary analysis	Completers Analysis including only data with first randomization	Only data collected are included regardless of intercurrent events. Kaplan-Meier method to take account of losses to follow-up.	Kaplan-Meier method
Proportion of participants with COVID-19 related hospitalization or death from any cause through Day 28.	Supplemental analysis for primary analysis	mITT including only data with first randomization	In the mITT population, participants that received a therapeutic COVID-19 mAb treatment post-baseline will be considered as an event for the endpoint (in addition to hospitalization and death due to any with mAb treatment date as the time of event). Kaplan-Meier method to take account of losses to follow-up.	Kaplan-Meier method
Proportion of participants with COVID-19 related hospitalization or death from any cause through Day 28.	Key secondary analysis	mITT1	All data collected will be included regardless of intercurrent events. Kaplan-Meier method to take account of losses to follow-up.	Kaplan-Meier method

Endpoint	Analysis Type	Population	Data Inclusion and Rules for Handling Intercurrent Events and Missing Data	Analysis Model
Proportion of participants with COVID-19 related hospitalization or death from any cause through Day 28.	Subgroup Analysis for primary endpoint	mITT	Subset analysis identified in Section 6.4.	Kaplan-Meier method
Time to sustained alleviation and time to sustained resolution of all targeted signs/symptoms	Secondary analysis	mITT & mITT1 & mITT2	All data collected will be included regardless of intercurrent events. Missing severity at baseline will be treated as mild.	Cox proportional hazard model
through Day 28.			Use stratification variables as in Section 3.5.	
Time to sustained alleviation of all targeted signs/symptoms through Day 28.	Subgroup Analysis of secondary endpoint	mITT	All data collected will be included regardless of intercurrent events. Missing severity at baseline will be treated as mild. Use stratification variables as in Section 3.5.	Cox proportional hazard model
			Subset analysis by baseline serology status and baseline viral load.	
Time to sustained resolution of all targeted signs/symptoms through Day 28.	Subgroup Analysis of secondary endpoint	mITT	All data collected will be included regardless of intercurrent events. Missing severity at baseline will be treated as mild. Use stratification variables as in Section 3.5.	Cox proportional hazard model
			Subset analysis by baseline serology status and baseline viral load.	
Proportion of participants with severe signs/symptoms attributed to COVID-19 through Day 28.	Secondary analysis	mITT, mITT1 & mTT2	All data collected will be included regardless of intercurrent events. Use BOCF/LOCF for missing data. Use stratification variables as in Section 3.5.	Kaplan Meier method Logistic regression

Endpoint	Analysis Type	Population	Data Inclusion and Rules for Handling Intercurrent Events and Missing Data	Analysis Model
Proportion of participants with severe signs/symptoms attributed to COVID-19 through Day 28.	Subgroup Analysis of secondary endpoint	mITT	All data collected will be included regardless of intercurrent events. Use BOCF/LOCF for missing data. Use stratification variables as in Section 3.5.	Logistic regression
Day 20.			Subset analysis by baseline serology status and baseline viral load.	
Duration of each targeted COVID-19 sign/symptom.	Secondary analysis	mITT, mITT1 & mTT2	All data collected will be included regardless of intercurrent events. Missing data will not be imputed.	Descriptive statistics
Progression to a worsening status in 1 or more self-reported COVID-19- associated symptoms through Day 28.	Secondary analysis	mITT, mITT1 & mTT2	All data collected will be included regardless of intercurrent events. Use BOCF/LOCF for missing data. Use stratification variables as in Section 3.5.	Logistic regression
Proportion of participants with a resting peripheral oxygen saturation ≥95% at Days 1 and 5.	Secondary analysis	mITT, mITT1 & mTT2	All data collected will be included regardless of intercurrent events. Missing data will not be imputed.	Breslow-Day test for Homogeneity of the Odds Ratios
Proportion of participants with any signs/symptoms attributed to COVID-19 through Week 12 & Week 24.	Additional follow-up analysis	mITT, mITT1 & mITT2	All data collected will be included regardless of intercurrent events. Missing data will not be imputed.	Descriptive Statistics
Proportion of participants with death (all cause) through Week 24.	Secondary analysis	mITT, mITT1 & mTT2	All data collected will be included regardless of intercurrent events. Missing data will not be imputed. Use stratification variables as in Section 3.5.	Logistic regression or Fisher Exact test (if appropriate)
Viral titers measured via RTPCR in nasopharyngeal samples at Day 1 and Day 5.	Sensitivity analysis (POC)	mITT, mITT1 & mTT2	All data collected will be included regardless of intercurrent events. Use baseline viral load (continuous).	ANCOVA analysis

Endpoint	Analysis Type	Population	Data Inclusion and Rules for Handling Intercurrent Events and Missing Data	Analysis Model
Viral titers measured via RT-PCR in nasal swabs over time.	Secondary analysis	mITT, mITT1 & mTT2	All data collected will be included regardless of intercurrent events. Use baseline viral load (continuous).	MMRM analysis
Number of COVID-19 related medical visits.	Secondary analysis	mITT, mITT1 & mTT2	All data collected will be included regardless of intercurrent events. Missing data will not be imputed.	Descriptive statistics (based on negative Binomial Distribution)
Number of days in hospital and ICU stay in participants with COVID-19 related hospitalization.	Secondary analysis	mITT, mITT1 & mTT2	All data collected will be included regardless of intercurrent events. Missing data will not be imputed.	Descriptive statistics

Appendix 2. Data Derivation Details

Appendix 2.1. Definition and Use of Visit Windows in Reporting

Visit Number	Visit Label	Definition [Day window]		
2	Baseline	= Day -2 to Day 1		
3	Day 3	= Day 3, with a window of ±1 days, (ie, days 2 to 4)		
4	Day 5	= Day 5, with a window of ±1 days, (ie, days 4 to 6)		
5	Day 10	= Day 10, with a window from days 7 to 11		
6	Day 14	= Day 14, with a window from days 12 to 17		
7	Day 21	= Day 21, with a window from 18 to 24		
8	Day 34	= Day 34, with a window from days 25 to 37		
9	Week 12	= Day 84, with a window of ±7 days, (ie, days 77 to 91)		
10	Week 24	= day 168 with a window of ±7 days, (ie, days 161 to 175)		

The following table defines the visit windows and labels to be used for reporting:

- Viral load: Baseline visit is set up according to study days of Day -2 to Day 1. The only viral load results collected after the start of dosing during the Baseline visit that are treated as Baseline data are those that were collected within 1 hour post start of dosing.
- Labs, COVID-19 Signs and Symptoms, Vital Signs and ECG: Baseline window will be Day -2 to Day 1, without any consideration to the time factor.
- When data from study Day 4 has an overlap between Day 3 and Day 5 windows, decision made is to assign the window according to the nominal visit. The rule will not be applicable to other study days 2 and 3 for Day 3 window, and days 5 and 6 for Day 5 window.
- If multiple readings fall into the same window, choose the one closer to the target day. If equidistant, then select the later one after the target day.
- Sign and symptom data at Week 12 & Week 24: No visit windowing will be applied. The nominal visits will be used.

Abbreviation	Term
AE	adverse event
AESI	adverse events of special interest
ANCOVA	analysis of covariance
BOCF	baseline observation carried forward
CDARS	Clinical Data Analysis and Reporting System
CI	confidence interval
ECG	electrocardiogram
E-DMC	external data monitoring committee
ET	early termination
FAS	full analysis set
FDA	Food and Drug Administration (United States)
LOCF	last observation carried forward
MedDRA	Medical Dictionary for Regulatory Activities
ITT	intent-to-treat
MMRM	mixed-effects model with repeated measures
PD	pharmacodynamic(s)
PK	pharmacokinetic(s)
PP	per-protocol
PT	preferred term
QTc	corrected QT
QTcF	corrected QT (Fridericia method)
SAE	serious adverse event
SAP	statistical analysis plan
SAS	Safety Analysis Set
SD	standard deviation
SOC	Schedule of Activities
SOP	standard operating procedure
WHO	World Health Organization

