Prior/concomitant medications	Х	Х		Х	Х	Х	Х	Х			Х	
 
All prescription and over-the-counter medications including vaccines taken by the participant within
 

Visit Identifier Abbreviations used in this table may be found in Appendix 12.	Screening	Baseline (Day 1)	Day 3	Day 5	Day 10	Day 14	Day 21	Day 34	LT Week 12	 ET (prior to Day 34)	Notes
Visit Window	Day -1 to Day 1	0 days	±1 day	±1 day	±1 day		±2 days	±3 days	±7 days	±5 days	
											
 
30 days before study entry (considered prior treatment) will be recorded.
 
Concomitant therapies will be collected through the Day 34 visit.
 
Refer to Section 6.8.
 

Adjunctive therapeutic procedures	X	Х		Х	Х	Х	Х	Х		Х	• Will be collected through the Day 34 visit.
Serious and nonserious ae monitoring	X	Х	[X]	Х	Х	Х	Х	Х		Х	
 
AEs should be assessed by means of a telemedicine visit if not feasible via an in-person visit
 
Refer to Section 8.3.
 

• Site staff should, in discussion with participants, determine the most appropriate location to conduct study visits, whether in-person or remotely by telemedicine. In-person visits should take place at the investigational site. If investigational site in-person visit is not feasible, then alternate venues may include the participant's home or an alternate, noninvestigational site location approved by the investigator. If an in-person visit is held at a location other than the investigational site, in certain situations the assigned HCP performing the visit may be unable to complete all assessments. In these cases, a telemedicine visit should also occur to perform the remaining assessments. Remote visits can be conducted using a telemedicine system approved for use at the site.

- Assessments indicated in brackets [X] will be performed only for in-person visits.
- Screening procedures may be done from Day -1 to Day 1. In many cases, all screening procedures can be completed in <24 hours. For these participants, screening procedures may be completed on the same calendar day as randomization and Baseline/Day 1 procedures, including first dose of study intervention.
- Baseline assessments should be performed before the administration of the first study intervention.
- Day 1 is the start of dosing.

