3.4. Baseline Variables

For viral load data, baseline visit is set up according to study days of Day -2 to Day 1. Only results that are within 1 hour post start of dosing will be treated as Baseline data. Laboratory assessments Signs and Symptoms, Vital Signs and ECG: Baseline window will be Day -2 to Day 1, without any consideration to the time factor.

The following baseline variables will be used in efficacy analyses. See below a list of derived baseline variables based on baseline viral load data:

- Baseline viral load defined as: $<10^4$ copies/mL vs $\ge 10^4$ copies/mL.
- Baseline viral load defines as: $<10^7$ copies/mL vs $\ge 10^7$ copies/mL.
- Baseline serology status defined as positive or negative.

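### The SAP's baseline window ignores dosing time: it contradicts 6.6.3 and 6.6.4 for vital signs and ECG, and lets a post-dose Day 1 laboratory value stand as baseline

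*SAP*

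**What the plan says.** SAP Appendix 2.1 gives one rule for four data types, namely laboratory, symptom, vital-sign and ECG data: "Baseline window will be Day -2 to Day 1, without any consideration to the time factor". SAP 3.4 repeats it in the body of the plan. When a window holds several readings, Appendix 2.1 says: "If multiple readings fall into the same window, choose the one closer to the target day". It then adds: "If equidistant, then select the later one after the target day". It names no target day for Baseline.

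Three other SAP rules bear on this:

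- Viral load (3.4) has a time limit: "Only results that are within 1 hour post start of dosing will be treated as Baseline data".
- Vital signs (6.6.3): "The measurement taken immediately prior to start of study drug will be used as the baseline".
- ECG (6.6.4): "Baseline will be defined as the mean of the pre-dose triplicates at the Baseline Visit".

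SAP 6.6.2 plans mean change from baseline and shift tables for laboratory data but defines no baseline of its own.

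Protocol 1.3 defines Day 1 as the start of dosing and instructs: "Baseline assessments should be performed before the administration of the first study intervention". Its laboratory notes say the same of baseline samples. Protocol 8.1.3 has the Day 1 diary completed before study intervention.

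**The concern.** For vital signs and ECG, the SAP holds two baseline rules that can select different values, and it states no precedence. Two programmers working from different sections could produce different change-from-baseline tables. ECG has a second mismatch: Appendix 2.1 selects one reading from a window, whereas 6.6.4 averages a triplicate.

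For laboratory data there is no competing SAP rule, so the time-blind window governs. The protocol's pre-dose instruction is not carried into the derivation. The SAP clearly foresaw post-dose Day 1 data, because it limits them for viral load.

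A baseline that already contains drug effect understates later change, and only in the active arm. Protocol 2.3.1 lists hemodynamic and inflammatory effects and TSH elevation as potential risks of the study drug. Protocol 8.3.8 makes the corresponding events AESIs. The shift tables in SAP 6.6.2 include TSH, free T4, fibrinogen, platelets, PT and aPTT.

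**Working it through.** The plan gives no figure to reproduce. The check applies each rule to the same readings and compares the value selected.

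**Inputs**

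- Window: Day -2 to Day 1, time ignored (SAP 3.4, Appendix 2.1).
- Selection: the reading closest to the target day (Appendix 2.1).
- Comparison rule: the last reading before study drug (SAP 6.6.3).
- Day 1 is the dosing day (Protocol 1.3).
- Assumption: the Baseline target day is Day 1, since none is stated.

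**Four hypothetical reading patterns**

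| Pattern | Appendix 2.1, tie to later reading | Appendix 2.1, tie to earlier reading | SAP 6.6.3 |
|---|---|---|---|
| A. Day -1 pre-dose and Day 1 pre-dose | Day 1 pre-dose | Day 1 pre-dose | Day 1 pre-dose |
| B. Day 1 pre-dose and Day 1 post-dose | Day 1 post-dose | Day 1 pre-dose | Day 1 pre-dose |
| C. Day -1 pre-dose and Day 1 post-dose | Day 1 post-dose | Day 1 post-dose | Day -1 pre-dose |
| D. Day 1 post-dose only | Day 1 post-dose | Day 1 post-dose | no baseline |

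Pattern A is what the protocol intends, and there the rules agree. In C and D they disagree however ties are broken. Only B depends on the tie sentence.

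**Where C and D could arise**

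- C is possible for vital signs, which are scheduled at both Screening and Baseline.
- D is possible for laboratory data, which are not required at screening.

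**Effect on a change score.** Let e1 be the drug effect present in a post-dose Day 1 reading, e5 the effect at Day 5, and f the share of active-arm participants whose baseline is post-dose.

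- With a pre-dose baseline, the drug's contribution to change at Day 5 is e5.
- With a post-dose baseline it is e5 - e1.
- Averaged over the active arm it is e5 - f × e1, so the loss is f × e1. Placebo has no drug effect to lose.

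The documents give neither f nor e1. At f = 0 (every site follows the protocol) nothing is lost. At f = 1, the upper limit, the loss is all of e1. In a shift table, a participant already abnormal on Day 1 because of the drug would be classed as abnormal at baseline and would not count as a shift.

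**The case against.** **Appendix 2.1 may only label visits.** It is introduced as visit windows for reporting. On that view it assigns records to the Baseline visit, and 6.6.3 and 6.6.4 then choose the value. This is a fair reading for vital signs and ECG. But 3.4 is the section on baseline variables; it names both data types and expressly sets time aside, and no precedence is stated. The reading does not help laboratory data, which have no specific rule.

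**Collection is already controlled.** Baseline readings should be pre-dose. After Baseline, the next scheduled vital signs and ECG are at Day 3 and the next laboratory tests at Day 5. The post-dose Day 1 sample that the schedule does plan, for PK, is outside this rule. This stands: only a late, repeat or unscheduled reading causes trouble. Scheduled ECGs also cover only the first 60 participants unless extended, and Protocol 9.3.6 plans no formal testing of laboratory or vital-sign safety data.

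**Stronger readings a reader might infer, which the documents do not support:**

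- That the tie rule makes the post-dose reading win whenever two Day 1 readings exist. The sentence speaks of a later reading after the target day, and Baseline has no stated target day. Applying it to two readings on one day is an interpretation.
- That the SAP contradicts itself for all four data types. Sections 6.6.3 and 6.6.4 cover vital signs and ECG only. For laboratory and symptom data the tension is with the protocol's instructions.
- That the protocol lists ECG changes as a risk. The risk table in 2.3.1 has no ECG entry, and 2.2.1 reports no drug-related ECG changes in the 15-day monkey study.
- That symptoms need the same strict pre-dose rule. Diary items cover the past 24 hours, so an entry made soon after the first dose mostly describes pre-dose time. Discarding it would trigger the rule that treats missing baseline severity as mild (SAP 5.3, 6.2.4). That would replace an observed score in time to sustained alleviation, a sequentially tested endpoint.

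**Conclusion.** The point holds as a minor drafting fault that should be corrected. For vital signs and ECG, SAP 3.4 and Appendix 2.1 contradict 6.6.3 and 6.6.4 with no stated precedence. For laboratory data, the only SAP rule admits a post-dose Day 1 value as baseline, although the protocol says samples should come first.

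The size cannot be computed: the loss is f × e1 and the documents give neither term. If sites follow the protocol, f should be small. The primary endpoint, COVID-19-related hospitalization or death through Day 28, uses none of these baselines and is unaffected. The conclusion takes Day 1 as the Baseline target day. It does not rest on the tie rule.

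**What to change.** In SAP 3.4 and Appendix 2.1:

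- **Vital signs and laboratory data:** define baseline as the last value at or before the first dose within Day -2 to Day 1.
- **ECG:** use the mean of the pre-dose triplicates, matching 6.6.4.
- **Untimed Day 1 values:** use one only if no timed pre-dose value exists.
- **Only post-dose Day 1 values:** flag these participants and report their number, rather than silently treating the values as baseline.
- **Symptoms:** use the pre-dose Day 1 diary entry when there is one. Otherwise keep the Day 1 entry, so that an observed score is not replaced by an assumed mild one.
- **Cross-references:** point 6.6.2, 6.6.3 and 6.6.4 to these definitions, and name the Baseline target day.

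The cost is SAP wording plus the need for dose and assessment times. Dose time is already required, because SAP 3.6.1 defines treatment-emergent events by the start date and time of study medication. The downside is that a few participants may have no valid baseline for safety changes; their number should be shown.
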